## Document History – Changes compared to previous final version of SAP

Date	Time point	Reason for update	Outcome for update	Section and title impacted (Current)
15-Jun-2020	FPFV	Creation of version 1.0	N/A - First version (based on protocol incl. amendment 1 from 10-Feb-2020 and amendment 2 from 19-May-2020)	N/A
31-Oct-2024	Prior to final analysis	Creation of version 2.0	Amendment 1 (based on protocols incl. amendment 3 from 08-Apr-2021 and amendment 4 from 22-Dec-2021 and amendment 5 from 08-Dec-2022)	

• Typos corrections and clarifications

• Naming change of study drug to investigational drug, study treatment or study treatment component, as needed.

• Based on Novartis' decision to terminate the program, the team was aligned to skip primary analysis and have a single final CSR, update the wording in section 1, 1.1, 2.1 and 2.2.

• Update to align with the protocol amendment 4:

- Sections 2.2 and 2.5.1, update DLT criteria and response criteria

• Update to align with the protocol amendment 5 and simplify analysis for leaning purpose:

- Update timing for primary endpoint across the entire document: all subjects should complete at least 12 cycles of treatment or discontinued treatment earlier, as compared to 7 cycles in original protocol.

- Sections 1.2, 2.6.1 and 2.9.3: 1) to use duration of CR and duration of CR/CRi instead of the terminologies of “RFS in CR patients” and “RFS in CR/CRi patients”; 2) add CR/CRh rate, duration

Date	Time point	Reason for update	Outcome for update	Section and title impacted (Current)
				
of CR/CRh and MRD negativity rate in subjects with CR/CRh as secondary endpoints; 3) Modify MRD negativity definition to request MRD-negative response (observed LAIP<0.1% via MRD samples) to be observed at or after morphological remission (bone marrow blast <5%) and update MRD analyses;
 
[REDACTED]
 

• Section 2.2: move IG analysis set from Section 2.8.3

• Section 2.3.1 add analysis on COVID-19 related protocol deviation as per new template.

• Section 2.4.1 remove analysis on cycle delayed and add analysis on cycle length by cycle.

• Section 2.4.2 remove the table for prior surgery and radiotherapies which will be listed only. Update analysis on transfusion: analyze only AML-related transfusions.

• Section 2.5.2 added to display via boxplot all assessments for disease response (incl. bone marrow, peripheral blood and extramedullary disease) and list some efficacy endpoints by subject (incl. BOR, OS, duration of response)

• Section 2.6 update to restrict the analysis of time-to-event secondary endpoints on MBG453 800mg Q4W dose level only.

• Section 2.6.1 add definitions of transfusion independence and dependence.

• Section 2.6.3 delete the rule of “two or more missing assessments” for all time-to-event endpoint analyses.

• Section 2.7.3 remove the shift tables for laboratory tests where grades are not defined by CTCAE v5.0.

• Section 2.7.4 add notable PR and QRS criteria in Table 2-4; Update vital signs

Date	Time point	Reason for update	Outcome for update	Section and title impacted (Current)
				
section to state that all patients will be analyzed regardless of their baseline value.
 

• Section 2.8 specify the analysis of PK endpoints by dose level of MBG453. Remove analysis for PK parameters and DDI.

• [REDACTED]

• [REDACTED]

• [REDACTED]

• [REDACTED]

• [REDACTED]

• [REDACTED]

• Appendix

- Update derivation of date of last exposure to investigational drug (MBG453), azacitidine, venetoclax and study treatment

- Add the derivations of cumulative dose, dose intensity and relative dose intensity of venetoclax

- Add the derivations of start/end date of a treatment cycle and cycle length

- [REDACTED]

- [REDACTED]

- Add the rules of derivation on last contact date

- Add ELN risk stratification categories (both 2017 and 2022) and the derivation algorithms

- Add ELN 2022 response categories in AML patients and its detailed derivation rules used for CRh-involved endpoints and analyses

## List of abbreviations

ADA	Anti-drug antibody
AE	Adverse event
AESI	Adverse events of special interest
ALT	Alanine aminotransferase
AML	Acute myeloid leukemia
AST	Aspartate aminotransferase
ATC	Anatomical therapeutic classification
BMA	Bone marrow aspirate
BMI	Body mass index
BP	Blood pressure
BSA	Body surface area
CI	Confidence interval
CR	Complete remission
CRh	Complete remission with partial hematologic recovery
CRI	Complete remission with incomplete hematologic recovery
CSR	Clinical study report
CTC	Common toxicity criteria
CTCAE	Common terminology criteria for adverse events
CV	Coefficient of variation
DDS	Dose-determining set
DLT	Dose limiting toxicity
DMS	Document Management System
eCRF	Electronic case report form
eCRS	Electronic case retrieval strategy
ECG	Electrocardiogram
ECOG	Eastern cooperative oncology group
EFS	Event free survival
ELN	European Leukemia Net
EORTC QLQ-C30	European Organisation for Research and Treatment of Cancer - Quality of Life Questionnaire
EOT	End of treatment
EQ-5D-5L	EuroQol Group - standardized measure of health status questionnaire
FAS	Full analysis set
HSCT	Hemopoietic stem cell transplantation
IG	Immunogenicity
LLOQ	Limit of quantification
MedDRA	Medical Dictionary for Drug Regulatory Affairs
MFC	Multiparameter Flow Cytometry
MLFS	Morphologic leukemia free state
MRD	Measurable residual disease
NGS	Next Generation Sequencing
OS	Overall survival

PD	Progressive disease
PFS	Progression-free survival
PGI	Patient global impression
PK	Pharmacokinetics
PR	Partial remission
PRO	Patient-reported outcomes
PT	Preferred term
QoL	Quality of life
Q4W	Every 4 weeks
RAP	Report and analysis process
RBC	Red blood cells
RFS	Relapse free survival
SAE	Serious adverse event
SAP	Statistical analysis plan
SD	Stable disease
SMQ	Standardized MedDRA queries
SOC	System organ class
TFLs	Tables, figures, listings
WHO	World Health Organization

## 1. Introduction

This statistical analysis plan (SAP) describes the planned analyses for the final Clinical Study Report (CSR) of the study CMBG453C12201, a phase II, open-label, single-arm, multi-center study of MBG453 in combination with azacitidine and venetoclax in adult subjects with newly diagnosed AML, who are not suitable for intensive chemotherapy and not planned for hematopoietic stem cell transplantation (HSCT).

As specified in the Section 12.7 of the study protocol, safety meetings were conducted during the safety run-in part of the study to assess the tolerability of MBG453 at two different doses (400 mg and 800 mg administered every 4 weeks) when given together with azacitidine + venetoclax before enrolling subject in the expansion part of the study. This SAP served as the basis for those analyses as well; however, a separate selection of tables, figures and listings (TFL) was done. In the meetings (one held on 22-Mar-2021, another on 26-Oct-2021), steering committee members agreed that there is no safety concern identified with the combination of MBG453 (400 mg or 800mg) with azacitidine and venetoclax, then MBG453 800 mg expansion cohort was opened and a total of 85 patients were enrolled and treated at 800 mg MBG453 (including those in safety run-in part).

[figure not shown]
The content of this SAP is based on the CMBG453C12201 protocol, Amendment 5 (08-Dec-2022). All decisions regarding the analysis, as defined in the SAP document, have been made prior to database lock.

However, Novartis made the decision in December 2023 to early terminate the sabatolimab (MBG453) clinical development program following the results of the primary analyses of phase II STIMULUS MDS1 and Phase III STIMULUS MDS2 studies – both studies failed to meet their primary objectives. As a consequence, this study was decided to be early terminated and the investigator letter about this decision was sent on 11-Jan-2024. Based on this decision, the primary analysis of CR rate after 12 cycles will be skipped, and the study data will be analyzed and reported based on all data up to final database lock (DBL) in the final CSR. This also meets the regulatory requirements.

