The main purpose of the present amendment is to revise the timing of the primary analysis (CR analysis) in order to capture potential late responders and more robust duration of response to study treatment. The CR rate analysis, initially planned when all subjects completed at least 7 treatment cycles or discontinued earlier, will now be performed when all subjects completed at least 12 treatment cycles or discontinued earlier. As recent publications highlighted the high variability of time to/duration of response in patients receiving venetoclax plus azacitidine; it is necessary to allow sufficient follow-up time before conducting the CR rate analysis ([Jonas et al 2022](#); [Pratz et al 2022](#)).

In addition, the following secondary endpoints were added: CR/CRh rate and duration of CR/CRh that will be derived by the Sponsor. These changes are made to reflect the updated ELN 2022 diagnosis and management of AML guidelines ([Döhner et al 2022](#)).

Furthermore, the following changes were made to the protocol:

Changes to the protocol

Changes to specific sections of the protocol are shown in the track changes version of the protocol using strike through red font for deletions and red underline for insertions.

- Updated glossary of terms and list of abbreviation with respect to latest Novartis protocol template and amended text
- Updated protocol summary with respect to changes in protocol body
- Section 1.1 – Background
 - Added data from a recent Phase III study on venetoclax+azacitidine combination ([DiNardo et al 2020](#))
- Section 1.2 – Purpose
 - Added reference to recent phase III trial ([DiNardo et al 2020](#))
- Section 2 – Objectives and endpoints
 - Table 2-1 – Objectives and related endpoints
 - Added timepoint for primary endpoint
 - Updated to use duration of CR and duration of CR/CRi instead of the terminologies of “RFS in CR patients” and “RFS in CR/CRi patients”, respectively.
 - CR/CRh rate, duration of CR/CRh and MRD negativity rate in subjects in CR/CRh were added as secondary endpoints
 - [REDACTED]
 - These changes are made to reflect the revised ELN 2022 AML guidelines. CRh related endpoints will be derived by the Sponsor
- Section 4.4.1 – Rationale for MRD assessments

- Data updated according to recent study update ([Pratz et al 2022](#))
- Reference to the revised ELN 2021 MRD guidelines was added
- [REDACTED]
- [REDACTED]
- [REDACTED]
- Section 4.5 – Purpose and timing of interim analyses/design adaptations

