
 Safety run in + Expansion: To assess the complete remission (CR) rate of MBG453, administered at 800 mg Q4W, in combination with azacitidine and venetoclax in subjects with AML not suitable for chemotherapy 	
 Proportion of subjects achieving a complete remission (CR) as per investigator assessment (Cheson et al 2003, Döhner et al 2017) will be determined when all subjects have completed at least 12 cycles of treatment with MBG453 + azacitidine + venetoclax or discontinued earlier.

 Safety run-in: To determine whether MBG453 at the two tested dose levels is not meeting overdose criteria when added to azacitidine + venetoclax in subjects with AML not suitable for chemotherapy. 	
 Incidence of DLTs between Cycle 1 Day 8 and end of cycle 2.
Secondary objective(s)	Endpoint(s) for secondary objective(s)

 To assess the MRD negativity rate 	
 Proportion of subjects with MRD negativity (a MRD negative sample determined by MFC-MRD and a bone marrow remission) in the full study population and/or any subgroup of interest (CR, CR/CRi, CR/CRh, etc.)

 To assess the CR/CRi rate and the duration of CR/CRi 	
 Proportion of subjects achieving a CR or CRi, as per investigator assessment (Cheson et al 2003, Döhner et al 2017) Time from the date of the first documented CR/CRi to the date of first documented relapse or progressive disease or death due to any cause, whichever occurs first, as per investigator assessment (Cheson et al 2003, Döhner et al 2017),

 To assess the duration of complete remission (CR) 	
 Time from the date of the first documented CR to the date of first documented relapse or progressive disease or death due to any cause, whichever occurs first, as per investigator assessment (Cheson et al 2003, Döhner et al 2017)

 To assess the CR/CRh rate and the duration of CR/CRh 	
 Proportion of subjects achieving a CR or CRh, as per derivation (Döhner et al 2022)

[figure not shown]
Objective(s)	Endpoint(s)

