12.4.1 Definition of primary endpoint(s)

For the safety run-in part, the primary endpoint is the incidence of DLTs between Cycle 1 Day 8 and the end of Cycle 2 of treatment for subjects in each cohort and included in the DDS.

The primary endpoint of the study (combining data from the safety run-in part and the expansion part) is the proportion of patients treated with MBG453 800 mg Q4W achieving a complete remission (CR) as per investigator assessment ([Cheson et al 2003](#), [Döhner et al 2017](#) and [Table 8-2](#)).

A subject with CR is classified as a responder.

The following events that could occur after enrollment, may affect the interpretation of the results:

- **Stopping study treatment (including due to toxicities):** all CR will be taken into account regardless of any study treatment interruption or permanent discontinuation.
- **Start of further anti-neoplastic therapy:** A subject with a first CR after the time he/she receives any further anti-cancer therapy would not be considered responder.
- **Hematopoietic stem cell transplantation (HSCT):** A subject with a first CR after the time he/she receives a SCT would not be considered responder.

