12.7 Interim analyses

No formal interim analysis is planned for this trial.

However, safety review meetings will be conducted after patients included in the first cohort (treated with MBG453 at the 400 mg Q4W) have completed 2 cycles of treatment, and assuming the 400mg Q4W dose is considered safe, after patients included in the second cohort (treated with MBG453 at 800 mg Q4W) have completed 2 cycles of treatment and prior starting the expansion part. The decision to escalated to the 800 mg Q4W dose and to continue with the MBG453 dose of 800 mg Q4W will be guided by a Bayesian analysis based on the incidence of dose limiting toxicity (DLT) data.

The primary analysis on CR rate will be performed after all subjects have completed 12 cycles of treatment with MBG453 + azacitidine + venetoclax or discontinued earlier. A final analysis will be performed after all subjects have completed the study which is planned 3 years after the last patient enrolled. Formal testing of the primary endpoint with full level alpha will be performed at the primary analysis. If required or requested by Health Authorities, updated analyses after the primary CR rate analysis may be conducted prior to the final analysis.

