**Table 1-1 Objectives and related endpoints**

Objective(s)	Endpoint(s)
Primary objective(s)	Endpoint(s) for primary objective(s)

Safety run in + Expansion: To assess the complete remission (CR) rate of MBG453, administered at 800 mg Q4W, in combination with azacitidine and venetoclax in subjects with AML not suitable for chemotherapy

Safety run-in: To determine whether MBG453 at the tested dose levels is not meeting overdose criteria when added to azacitidine + venetoclax in subjects with AML not suitable for chemotherapy.

	

Proportion of subjects achieving a complete remission (CR) as per investigator assessment (Cheson et al 2003, Döhner et al 2017) will be determined when all subjects have completed at least 12 cycles of treatment with MBG453 + azacitidine + venetoclax or discontinued earlier.

Incidence of dose limiting toxicities (DLT) between Cycle 1 Day 8 and end of cycle 2.

Secondary objective(s)	Endpoint(s) for secondary objective(s)

To assess the measurable residual disease (MRD) negativity rate

	

Proportion of subjects with MRD negativity (a MRD negative sample determined by Multiparameter Flow Cytometry (MFC)-MRD and a bone marrow remission) in the full population and/or any subgroup of interest (CR, CR/CRi, CR/CRh)

Objective(s)	Endpoint(s)

 
To assess the CR/CRi rate and the duration of CR/CRi
 
	
 
Proportion of subjects achieving a complete remission (CR) or complete remission with incomplete hematologic recovery (CRi), as per investigator assessment (Cheson et al 2003, Döhner et al 2017)
 
Time from the date of the first documented CR/CRi to the date of first documented relapse or progressive disease or death due to any cause, whichever occurs first, as per investigator assessment (Cheson et al 2003, Döhner et al 2017)
 

 
To assess the duration of complete remission (CR)
 
	
 
Time from the date of the first documented CR to the date of first documented relapse or progressive disease or death due to any cause, whichever occurs first, as per investigator assessment (Cheson et al 2003, Döhner et al 2017)
 

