Progressive Disease (PD)	
Evidence for an increase in bone marrow blast percentage and/or increase of absolute blast counts in the blood
 
 
• >50% increase in marrow blasts from maximum remission or baseline ,whatever is lower (a minimum 15% point increase is required in cases with <30% blasts at baseline; or persistent marrow blast percentage of >70% over at least 3 mo; without at least a 100% improvement in ANC to an absolute level (>0.5 X 10^9/L [500/µL], and/or platelet count to >50 X 10^9/L [50 000/µL] nontransfused); or
 
• >50% increase in peripheral blasts (WBC X % blasts) to >25 X 10^9/L (>25 000/ µL) (in the absence of differentiation syndrome); or
 
• New extramedullary disease
 

Stable disease (SD)	Absence of CR, CRi, PR, MLFS, and criteria for PD or relapse are not met
Relapse from CR or CRi	
Only in patients with a CR or CRi . Any of the following:
 
 
• Reappearance of blasts in peripheral blood
 
 
OR
 
 
• ≥ 5% blasts in bone marrow
 
 
OR
 
 
• (Re-)appearance of extramedullary disease
 

Unknown	In case the response assessment was not done or the assessment was incomplete

The investigator does not determine best overall response, he/she is assessing only the response based on the given bone marrow and peripheral blood data, as well as on the presence or absence of extramedullary disease. The best overall response is the best disease response recorded from the start of the treatment until the first occurrence of relapse or death. Best response will be derived by Novartis for each subject as one of the following: CR, CRI, MLFS, PR, SD, PD, and unknown for all other cases.

The primary estimand related to CR rate is described by the following attributes:

1. Population: subjects with newly-diagnosed acute myeloid leukemia (AML) who are not suitable for intensive induction chemotherapy as defined by inclusion/exclusion criteria and who are assigned to the MBG453 800 mg Q4W dose level.
2. Primary variable: percentage of subjects achieving a complete remission (CR) as per investigator assessment.

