#### **CR analysis (safety run-in and expansion parts):**

The sample size calculation is based on the Complete Remission (CR) rate (primary efficacy endpoint) observed in subjects treated with MBG453 at 800 mg Q4W (from both safety run-in and expansion parts). The hypotheses to be tested and details of the testing strategy are described in [Section 2.5.2](#).

Based on available data ([Pollyea D. et al 2018](#)), the CR rate with the combination azacitidine+venetoclax is expected to be around 50%. The first criteria to declare the trial successful is to test if the CR with MBG453 in combination with azacitidine and venetoclax is superior to 50% (statistical significance). The second criteria is to obtain a minimum estimated effect size of at least 61% for the CR (clinical relevance).

The Bayesian formulation of this dual criterion design can be expressed as below:

- Bayesian statistical significance: probability for a positive treatment effect (i.e. CR rate  $\geq 50\% | \text{data}$ )  $\geq 0.975$
- Clinical relevance: posterior median of CR rate  $\geq 61\%$

With two criteria stated above the minimally required sample ( $n_{\min}$ ) size is 76 and the final sample size was set to 80. For 80 subjects, the table below shows data scenarios (number of responders) with respective inferential results and decisions. The minimum number of responders to declare this trial successful (both statistical significance and clinical relevance met) is 49 out of 80 subjects (61%). Based on simulations (Table 3-1), a total of 49 responders out of 80 results in a posterior median CR rate of 61.1% and a posterior probability for a positive effect ( $\text{CR} > 50\%$ ) of 0.978. If the number of responders is less than 49, both criteria are missed (NO-GO). A uniform informative Beta (1,1) prior with mean 50% has been used in these calculations.

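### The SAP moves the formal CR test from the protocol's 12-cycle data cut-off to database lock, keeps the success rule, and plans no CR result at the protocol's cut-off

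*SAP*

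**What the plan says.** **Protocol.** Section 12.4.1 defines the primary variable as "the proportion of patients treated with MBG453 800 mg Q4W achieving a complete remission (CR) as per investigator assessment". It sets no time limit per subject. Table 2-1 says that this proportion "will be determined when all subjects have completed at least 12 cycles of treatment with MBG453 + azacitidine + venetoclax or discontinued earlier". Section 12.4.2 uses that milestone as the data cut-off for the CR analysis. Section 12.7 adds: "Formal testing of the primary endpoint with full level alpha will be performed at the primary analysis". It lists a later final analysis as a separate event.

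**Amendment 5.** The milestone moved from 7 to 12 cycles when all 90 subjects were already enrolled. One stated aim was "in order to capture potential late responders".

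**SAP.** After the development program was terminated, Section 1 states that "the primary analysis of CR rate after 12 cycles will be skipped". Sections 1, 1.1 and 2.1 have the study analysed on all data up to final database lock. The estimand in Section 2.5.1 keeps the variable as "percentage of subjects achieving a complete remission (CR) as per investigator assessment". Section 2.5.2 keeps both success criteria: posterior probability of at least 97.5% that the CR rate exceeds 50%, and posterior median of at least 61%. The supportive CR analyses in Section 2.5.4 cover only the 400 mg group and all FAS subjects.

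Two parts of the SAP were not brought into line. Table 1-1 still says that the CR proportion "will be determined when all subjects have completed at least 12 cycles of treatment", and Section 4, which is the place for departures from the protocol's analyses, is marked as not applicable. Section 3 gives the success count for 80 subjects, while Section 1 reports 85 treated at 800 mg.

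**The concern.** The protocol fixes one date for the single formal test. The SAP replaces it with a later one and leaves the threshold alone. CR counts if it is ever reached, whether or not study treatment continues, and protocol 8.3.1 and 9.1.1.2 keep marrow assessments going after treatment stops. Later data can therefore add responders but not remove them, and the comparison is with a fixed 50%.

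The success decision would then rest on a cut-off that the protocol did not assign to it, and no planned output would let a reader see the decision at the cut-off that the protocol did assign. The sponsor's own reason for Amendment 5 shows that late responses were thought possible in this open-label, investigator-assessed trial.

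**Working it through.** **1. Reproduce the plan's figures (n=80).** With the Beta(1,1) prior of SAP 2.5.2 and r responders among n, the posterior is Beta(1+r, 1+n−r). Success needs P(CR>50%) ≥ 0.975 and posterior median ≥ 61%.
- r=48: median 59.8%, probability 0.963. Fails.
- r=49: median 61.1%, probability 0.978. Succeeds.
- Type I error: P(X≥49 | 80, 0.50) = 0.0283. Power: P(X≥49 | 80, 0.65) = 0.7951.

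These agree with SAP Tables 3-1 and 3-2 (49/80, 2.8%, 79.5%). The design arithmetic is sound.

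**2. The same rule at the actual n=85 (SAP Section 1).**
- 49/85: median 57.5%, probability 0.920. Fails.
- 51/85: median 59.8%, probability 0.967. Fails.
- 52/85: median 61.0%, probability 0.980. Succeeds.
- Type I error: P(X≥52 | 85, 0.50) = 0.0251. Power: P(X≥52 | 85, 0.65) = 0.8039.

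So 52 CRs are needed. If the count at the milestone were 51, one further CR before lock would decide the trial.

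**3. How far apart the cut-offs can be.** All subjects were enrolled by 08-Dec-2022 (Amendment 5). For a subject starting that day without delays, 12 × 28 = 336 days ends on 09-Nov-2023. SAP version 2.0 is dated 31-Oct-2024 and says that its decisions precede lock. That date is 693 days after 08-Dec-2022, or 693/28 = 24.75 nominal cycles. The nominal gap is 693 − 336 = 357 days. This is only indicative: delayed cycles would push the milestone later, and data collection may have ended before lock.

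**4. Effect on the decision.** The documents give no rate of first CR between the two cut-offs, so the following is an assumption. Let p be the CR rate at the milestone and a the proportion of all subjects who first reach CR after it and before lock. The chance of success at lock is P(X≥52 | 85, p+a).

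| a | p = 50% | p = 60% |
|---|---|---|
| 0% | 2.5% | 45.9% |
| 1% | 3.8% | 53.4% |
| 2% | 5.6% | 60.9% |
| 3% | 8.0% | 68.0% |

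At p = 50%, a = 1, 2 or 3% of all subjects is 2, 4 or 6% of those not yet in CR. With a = 0 the two cut-offs give the same result.

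**The case against.** The strongest reply is that the endpoint is unchanged, and this stands. A reader might infer that the SAP tests a different endpoint from the protocol's. It does not: variable, dose group, response criteria and intercurrent-event rules match. Twelve cycles is a minimum-follow-up trigger for a study-level cut, and a lock after that point also satisfies the wording of Table 2-1. Early enrollees' CRs after their own Cycle 12 would already count at the protocol's cut-off: 29 subjects were enrolled by 22-Dec-2021, 687 days before 09-Nov-2023. A per-subject Cycle-12 window would itself depart from the protocol.

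Other stronger readings also fail.
- Not every CR up to lock counts. SAP 2.5.3 excludes a first CR after new anti-neoplastic therapy or HSCT.
- Nothing shows that CR results drove the change. SAP Section 1 ties it to two other trials that missed their primary objectives, says that decisions were made before lock, and discloses the skip, as does the document history.
- There is no repeated testing, because the test is still done once.
- The one-way direction applies to the same subjects at two cut-offs, not to a comparison with a trial that had not been terminated. The investigator letter of 11-Jan-2024 falls on day 399. A subject with more than 399 − 336 = 63 days of accumulated delay could have been stopped before Cycle 12.
- The documents give no follow-up horizon for the 50% benchmark, so treating it as the rate at the milestone is part of the assumption.

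Finally, the operative rule in SAP 2.5.2 is stated as a probability and a median, so it applies at n=85 without amendment. The 49/80 figure records the planned design. It becomes misleading only if it is read as the count for this trial.

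These replies leave one point untouched: protocol 12.7 assigns the formal test to the 12-cycle analysis, and the SAP plans no result there.

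**Conclusion.** The point holds as a change of data cut-off and of the analysis that carries the formal test. It is not a change of endpoint. The later cut-off can favour success but cannot count against it in the same subjects, data corrections aside. The SAP neither shows the result at the protocol's cut-off nor declares the change in Section 4, and its Table 1-1 still describes the skipped timing.

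The size is unknown. Under the stated assumption of 0 to 3% late first CRs and a milestone rate of 50%, the chance of success runs from 2.5% to 8.0%. If there are no late CRs, nothing changes. The exact part is the threshold: 52 of 85, with one CR separating failure from success.

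**What to change.** 1. In SAP 2.5.2 and 2.5.4, report the CR rate and both success criteria using data up to the date on which the study-level 12-cycle milestone was met, beside the result on all data to lock. State which of the two carries the formal decision.
2. Declare the cut-off change in SAP Section 4 and align the wording of Table 1-1.
3. In SAP Section 3, keep the n=80 design figures and add those for n=85: 52 responders needed, type I error 2.5%, power 80.4% at a true CR rate of 65%.

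Do not impose a per-subject Cycle-12 window. A CR rate by C8D1, for which SAP 2.6.1 already defines a window under EFS, is optional.

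The cost is some SAP wording and a few table rows from data already collected. The milestone result may be slightly less favourable than the all-data one.
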